### **5.3. Study objectives**

#### Primary objective:

To determine the safety and toxicology profile of plitidepsin at each dose level administered in patients admitted for COVID-19 according to the proposed administration scheme.

#### Secondary objectives:

- To assess the efficacy of plitidepsin in patients with COVID-19 at the proposed dose levels by:
  - o Change in SARS-CoV-2 viral load from baseline
  - o Time until negative detection of SARS-CoV-2 by PCR
  - o Cumulative incidence of disease severity. The evaluation will be based on:
    - Mortality
    - Need for invasive mechanical ventilation and/or ICU admission
    - Need for non-invasive mechanical ventilation
    - Need for oxygen therapy
- Selection of the recommended dose levels of plitidepsin for a phase II/III efficacy study

## **6. STUDY DESIGN**

### **6.1. Design**

Multicentre, randomised clinical trial with three treatment arms.

Three cohorts of 9 patients will be included in the study. Each of the cohorts of 9 patients will include 3 arms (A, B, and C) at different dose levels with 3 patients in each arm, up to a maximum of 27 patients evaluable for safety.

The established dosage levels are as follows:

- Arm A) 1.5 mg of plitidepsin administered as a 1.5-hour infusion, once a day for 3 consecutive days.
- Arm B) 2.0 mg of plitidepsin administered as a 1.5-hour infusion, once a day for 3 consecutive days.
- Arm C) 2.5 mg of plitidepsin administered as a 1.5-hour infusion, once a day for 3 consecutive days.

ARM	Dosage level	Daily dose (mg)	Total dose (mg)
Arm A	1	1.5 mg x 3 days	4.5 mg
Arm B	2	2.0 mg x 3 days	6.0 mg
Arm C	3	2.5 mg x 3 days	7.5 mg

Recruitment will be sequential in each of the three arms. The first cohort of 3 patients in arms B and C (2.0 mg and 2.5 mg) will not open until the data have been analysed for the first 3 patients at the dose level immediately below (arms A or B) without observing any unacceptable toxicity, taking into account the data of the three patients included in each arm with a 12-day follow-up from the end of treatment (day +15 from the start of treatment).

When patients are to be included at more than one dose level (arm), patients will be randomised in a 1:1 or 1:1:1 ratio as appropriate.

The following criteria have been established to continue the inclusion of patients in the different arms:

- If 0-1 of the first three patients treated with the dose of 1.5 mg x 3 days experience any adverse event classed as grade 3 or higher within twelve days after administration of the last dose, three additional patients will be enrolled in the 1.5 mg arm and recruitment of the first three patients in the 2.0 mg arm will start. Recruitment in the 2.5 mg arm will be opened after it has been proven that only 0-1 of the three patients in the first cohort in the 2.0 mg arm have grade 3 or greater toxicity within twelve days of follow-up after administration of the last dose of 2.0 mg.
- 
- If 2 or more patients in any of the arms present an adverse event classed as grade 3 or higher, the sponsor will interrupt the recruitment of new patients and will jointly assess with the Spanish Agency of Medicines and Medical Devices whether or not to continue recruitment in that arm and in arms with a higher dose.

Intra-patient dose change/increase is not allowed.

Once the 27 patients (9 at each dose level) contemplated in the study protocol have been included, an extension period will be opened to include 18 additional patients (6 at each plitidepsin dose level) to extend the collection of safety information on the different doses and additionally to collect efficacy data. After this extension period, data will be available for 15 patients at each plitidepsin dose level.

During the extension period, patients will be randomised in a 1:1:1 ratio as appropriate to each dose level (arm).

During the extension period of the study, if in any of the arms, 2 or more patients present an adverse event classed as grade 3 or higher related to plitidepsin, the sponsor will interrupt the recruitment of new patients at that dose level and higher, and will assess jointly with the Spanish Agency of Medicines and Medical Devices the convenience of continuing recruitment in that arm and in arms with a higher dose. Additionally, the sponsor will forward weekly follow up records to the Spanish Agency of Medicines and Medical Devices, with the information of all the adverse event classed as grade 3 or higher, reported, whether or not related to plitidepsin, for review and joint assessment if necessary.

After the joint evaluation of the safety and efficacy data obtained in the present study between the sponsor and the Spanish Agency of Medicines and Medical Devices, the recommended dose level will be selected to evaluate the efficacy of the treatment in patients with COVID-19 in a subsequent randomised phase II/III study.

The final statistical analysis that will be the basis of the final report of the study will be done on the total population of 45 patients once the extension of the study has been completed. The data of the first 27 patients will be analysed in an intermediate statistical analysis.

## **6.2.Primary endpoint**

### Primary endpoint:

To determine the safety and toxicological profile of plitidepsin at each dose level administered in patients admitted for COVID-19, the following endpoints will be analysed:

- Frequency of the following  $\geq$  grade 3 adverse events according to the NCI-CTCAE criteria v 5.0 at 3, 7, 15 and 31 days:
  - Haematological
    - Neutropenia
    - Thrombopenia
    - Anaemia
    - Lymphopenia
  - Non-haematological
    - CPK increase
    - ALT and/or AST increase
    - Total bilirubin or direct bilirubin increase
    - Neurotoxicity

- QT-QTc interval prolongation
- Other  $\geq$  grade 3 adverse events
- Percentage of patients in which treatment cannot be completed and reasons.
- Percentage of patients with AEs and SAEs at days 3, 7, 15 and 31.
- Changes from baseline (day -1 or day 1 before administration of the study drug) in haematological and non-haematological parameters on days 3, 7, 15 and 31.
- Percentage of patients with ECG abnormalities on days 2, 3, 4, 5, 6, 7, 15 and 31.

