### **7.2. Exclusion criteria**

1. Patients participating in another clinical trial for COVID-19 infection.
2. Patients receiving treatment with antivirals, interleukin-6 receptor inhibitors and immunomodulatory drugs for COVID-19.
3. Patients who are receiving treatment with chloroquine and derivatives.
4. Evidence of multi-organ failure.
5. Patients requiring support with mechanical ventilation (invasive or non-invasive) at the time of inclusion.
6. D-dimer  $> 4 \times$  LSN.
7. Hb  $< 9$  g/dl.
8. Neutrophils  $< 1000/\text{mm}^3$ .
9. Platelets  $< 100,000/\text{mm}^3$ .
10. Lymphopenia  $< 800/\mu\text{l}$ .
11. GOT / GPT  $> 3 \times$  ULN.
12. Bilirubin  $> 1 \times$  ULN.
13. CPK  $> 2.5 \times$  ULN.

14. Creatinine clearance <30 ml/min.
15. Troponin elevation > 1.5 x ULN.
16. Clinically relevant heart disease (NYHA > 2).
17. Clinically relevant arrhythmia or previous history/presence of prolonged QT-QTc interval  $\geq$  450 ms.
18. Pre-existing neuropathies of any type  $\geq$  grade 2.
19. Hypersensitivity to the active substance or to any of the excipients (macrogolglycerol ricinoleate and ethanol)
20. Patients who require or are being treated with strong CYP3A4 inhibitors and inducers (See annex 5).
21. Patients who for any reason should not be included in the study according to the evaluation of the research team.

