## 10. EVALUATION CALENDAR

	Baseline	Day 1	Day 2	Day 3	Day 4	Day 5	Day 6	Day 7	Day 15 (± 1 day)	Day 31 (± 3 days) 
Informed consent 	X									
Selection criteria 	X									
Medical record	X									
Vital signs 	X	X	X	X	X	X	X	X	X	X
Demographics	X									
Physical examination	X									
Electrocardiogram 	X	X	X	X	X	X	X	X	X	X
Complete blood count 	X	X*	X	X	X	X	X	X	X	X
Biochemistry 	X	X*	X	X	X	X	X	X	X	X
Coagulation 	X	X*	X	X	X	X	X	X	X	X
C-reactive protein 	X	X*	X	X	X	X	X	X	X	X
Viral load 	X				X			X	X	X
PCR COVID-19 	X				X			X	X	X
Chest x-ray 	X	Based on clinical criteria								
Pregnancy test 	X									
Treatment		X	X	X						
Other pharmacological treatments for COVID-19 			X	X	X	X	X	X	X	X
Adverse events 	X	X	X	X	X	X	X	X	X	X

- \* It will not be necessary to repeat the tests on day 1 if they were carried out in the 24 hours prior to administration of plitidepsin.
- 1 The patient will sign the informed consent before undergoing any specific study procedure that is not part of normal clinical practice.
  - 2 The patient must meet all the inclusion criteria and none of the exclusion criteria in order to be included in the study.
  - 3 Vital signs will be measured **every 8 hours** or every nursing shift until discharge: temperature, blood pressure, heart rate, respiratory rate, O2 saturation (including oxygenation method). Once the patient has been discharged, a single measurement of vital signs will be made at the study visits detailed in the table.
  - 4 The electrocardiogram will be performed during the baseline visit and on days 1, 2, 3, 4, 5, 6, 7, 15 and 31 from the start of treatment with plitidepsin. The PR interval and the QT interval will be measured.
  - 5 Complete blood count on days 1, 2, 3, 4, 5, 6, 7, 15 and 31.
  - 6 Basic biochemistry on days 1, 2, 3, 4, 5, 6, 7, 15 and 31. It will include transaminases, bilirubin, alkaline phosphatase, LDH, CK, ferritin and troponin.
  - 7 Coagulation on days 1, 2, 3, 4, 5, 6, 7, 15 and 31, including D-dimer.
  - 8 C-reactive protein on days 1, 2, 3, 4, 5, 6, 7, 15 and 31.

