### **12.4. Analysis of the primary endpoint**

The safety analysis will be performed in the safety population, that is, in patients who have received at least one dose of treatment. Patients will be analysed in the administered treatment arm.

Safety and tolerability analyses will be presented by treatment arm as well as by treatment arm according to age group (<65 years; ≥65 years). Adverse events will be coded using the latest version of the MedDRA dictionary and assessed using the NCI-CTCAE criteria v. 5.0.

The number and percentage of patients presenting the following ≥ grade 3 adverse events will be provided, according to the NCI-CTCAE criteria v. 5.0 at 3, 7, 15 and 31 days after the start of study treatment:

- Haematological
    - Neutropenia
    - Thrombopenia
    - Anaemia
    - Lymphopenia
  - Non-haematological
    - CPK increase
    - ALT and/or AST increase
    - Total bilirubin or direct bilirubin increase
    - Neurotoxicity
    - QT-QTc interval prolongation
  - Other ≥ grade 3 adverse events
- The number and percentage of patients in whom treatment cannot be completed and the reasons will be provided.
  - The number and percentage of patients with AEs and SAEs will be provided at 3, 7, 15 and 31 days.
  - The evolution of haematological and non-haematological parameters from the baseline visit on days 3, 7, 15 and 31 will be provided.

*CONFIDENTIAL*

- The number and percentage of patients with ECG abnormalities on days 1, 2, 3, 4, 5, 6, 7, 15 and 31 will be provided. Any alterations detected will be described in detail.

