- Rheumatic disorder (Yes/No).
- Moderate or severe liver disease (Yes / No).
- Mild liver disease (Yes/No).
- Dementia (Yes/No).
- Malnutrition (Yes/No).
- Chronic neurological disorder (Yes / No).
- Smoker (Yes/No).
- Malignant neoplasm (Yes/No).
- Chronic hematological disease (Yes / No).
- AIDS / HIV (Yes / No).
- Obesity (define by medical staff) (Yes/No).
- Other risk factors (Yes / No). If so, the description of the specified factors will be detailed.

e) Vital signs at baseline

- SBP (mmHg) (continuous).
- DBP (mmHg) (continuous).
- Heart rate (l.p.m.) (continuous).
- Respiratory rate (r.p.m.) (continuous).
- Temperature (°C) (continuous).
- Saturation O₂ (%) (continuous).
- Saturation (Room air/Oxygen therapy/Not available). In the case of oxygen therapy, the following will be described:
 - Oxygen therapy type (Nasal glasses; Simple mask; Venturi mask; Reservoir mask; Other). In case of other a detailed listing will be provided.
 - Flow (L/min) (continuous).
 - FiO₂ (%) (continuous).
 - PaO₂ (mmHg) (continuous)
 - PaO₂/FiO₂ o SaO₂/FiO₂ (continuous).
- Chest X-ray (Yes/No). if so, the following will be described:
 - X-ray result (Normal/Abnormal). In case of abnormality, the abnormality will be detailed (Unilateral Pneumonia / Bilateral Pneumonia / Other). In case of other abnormality, the description of the abnormalities will be provided.
- Electrocardiogram (Yes / No). If so, it will be described:
 - Result (Normal / Abnormal: Not clinically significant or Abnormal: clinically significant). In case of abnormality, the description of the abnormalities will be provided. (QT interval prolongation / PR interval prolongation / other alteration). In case of other alteration, the description of the other alteration will be provided.

f) Viral load (log copies / mL)

g) Summary of Demographic and Other Baseline Characteristics

- Age, median (range) years

- Gender, % male
- Median (range) time from symptom onset to first plitidepsin administration, days
- Number of comorbidities, n (%) (none, one, two or more)
- Comorbidities, n (%) (Cardiac disease, Kidney disease, Liver disease, Lung disease (COPD), Asthma, Diabetes, Hypertension, Obesity)
- Clinical status at randomization, n (%)
- Vital signs, median (range) (Body temperature, °C, Systolic blood pressure, mmHg, Diastolic blood pressure, mmHg, Heart rate, bpm, Respiratory rate, bpm, SpO2 B, %, On oxygen at baseline, n (%))

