7.3 Other safety evaluation

The analysis will be performed on the safety population by treatment arm as well as by treatment arm based on age groups (<65 years; ≥ 65 years). The following variables are described at baseline and on days 1, 2, 3, 4, 5, 6, 7, 15 and 31 of study treatment:

- Number and percentage of patients with alterations in the chest X-ray and the indicated anomalies will be described. The following variables will be described: no change, improvement, worsening.
- Evolution of the chest X-ray result per patient.
 - N (%) of patients with improvement in radiography on days 7, 15 and 31 after the first dose of plitidepsin
 - N (%) of patients with worsening in radiography on days 7, 15 and 31 after the first dose of plitidepsin
 - N (%) of patients with no changes in radiography on days 7, 15 and 31 after the first dose of plitidepsin
- Number and percentage of patients with ECG alterations and the detected alterations will be described.
- A list with the evolution of SaO₂ in each of the controls carried out on the patients will be provided, indicating the type of saturation (air in the room / oxygen therapy / not available).
- Change in Vital Signs (median and range) from Baseline through Day 31. Calculated using the mean value when there were more than one assessment per day will be used for blood pressure measurements. Worst value per patient, per day, will be used for the rest of measurements.
 - Blood pressure, diastolic (mm Hg)
 - Blood pressure, systolic (mm Hg)
 - Heart rate (beats per minute)
 - Respiratory rate (breaths per minute)
 - pSO₂ by pulse oximetry (%) (Room-air)

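### The primary ECG component counts every abnormal ECG on the day without separating new or worsened findings from those present at entry, and dosing-day ECGs are not timed to the infusion

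*Protocol*

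**What the plan says.** **Endpoint.** Protocol 6.2 (repeated in 1.11 and SAP 2.6) lists, as part of the primary endpoint, "Percentage of patients with ECG abnormalities on days 2, 3, 4, 5, 6, 7, 15 and 31". The item just above it, for laboratory parameters, is expressed as change from baseline; the ECG item is not.

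**Analysis.** Protocol 12.4 adds Day 1: "The number and percentage of patients with ECG abnormalities on days 1, 2, 3, 4, 5, 6, 7, 15 and 31 will be provided". It continues: "Any alterations detected will be described in detail". SAP 7.3 plans "Number and percentage of patients with ECG alterations and the detected alterations will be described", by treatment arm and age group, under the lead-in "The following variables are described at baseline and on days 1, 2, 3, 4, 5, 6, 7, 15 and 31". None of these texts defines an abnormality or restricts the count to new or worsened ones.

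**Entry.** Protocol 7.2 excludes heart disease above NYHA class 2 and "Clinically relevant arrhythmia or previous history/presence of prolonged QT-QTc interval" of 450 ms or more. Other ECG findings are allowed. SAP 5.2 provides for them, coding the baseline ECG as "Result (Normal / Abnormal: Not clinically significant or Abnormal: clinically significant" and listing PR prolongation and other alterations among the descriptions.

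**Schedule.** Footnote 4 to the calendar in Protocol 10 says "The electrocardiogram will be performed during the baseline visit and on days 1, 2, 3, 4, 5, 6, 7, 15 and 31", with PR and QT measured. It gives no time relative to the 1.5-hour infusion on Days 1 to 3.

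**The concern.** The primary objective is the safety profile at each dose level, and these data feed the choice of dose for a phase II/III study. A patient who enters with a lasting, non-significant abnormality is counted on every study day in the same way as a patient whose ECG became abnormal after dosing. If such patients are common, the percentages rise in all arms and the arms look more alike than they are.

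Timing is a second gap. A site that records each dosing-day ECG before the infusion follows the calendar exactly, yet never looks at the hours just after an infusion. Protocol 5.2 itself describes plasma concentration as the relevant measure for safety. A Day 1 ECG without a stated time may be a second baseline or a first on-treatment reading, and the documents disagree on whether Day 1 belongs to the endpoint.

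**Working it through.** **1. The plan's own figure.** Three arms of 9 plus an extension of 6 per arm: 3 × 9 + 3 × 6 = 45, or 15 per arm. This agrees with Protocol 6.1 and 12.1. No expected ECG rate is stated.

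**2. What two percentages leave open.** SAP 7.3 gives the percentage abnormal at baseline and on each day. Suppose x of 15 are abnormal at baseline and y of 15 on a later day, with no missing ECGs. The number abnormal that day who were normal at entry lies between max(0, y − x) and min(y, 15 − x).

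- x = 3, y = 3: from 0 to 3 patients. Exact 95% intervals: 0/15 gives 0% to 21.8%; 3/15 gives 4.3% to 48.1%.
- x = 5, y = 6: from 1 to 6 patients. Exact 95% intervals: 1/15 gives 0.2% to 31.9%; 6/15 gives 16.3% to 67.7%.

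The counts here are hypothetical. The point is that the two percentages alone do not fix the number newly abnormal.

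**3. Share of the count that comes from entry.** Let b be the share abnormal at entry, q the share of those still abnormal on the day, and i the rate of new abnormality among those normal at entry. All three are assumed.

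- Percentage on the day = q·b + (1 − b)·i
- Share due to entry = q·b / [q·b + (1 − b)·i]

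For b from 5% to 40% and i from 5% to 30%, the entry share runs from 15% to 93% with q = 1, and from 11% to 90% with q = 0.7. With q = 1 it passes one half when b > i/(1 + i): 4.8%, 9.1%, 16.7% and 23.1% for i = 5%, 10%, 20% and 30%.

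**4. Dilution of a dose contrast.** Take i = 5% in one arm and 30% in another, with q = 1 and the same b in both. The difference becomes (1 − b) × 25 points.

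| b | Lower arm | Higher arm | Difference | Ratio |
|---|---|---|---|---|
| 0% | 5% | 30% | 25 points | 6.0 |
| 20% | 0.20 + 0.80 × 0.05 = 24% | 0.20 + 0.80 × 0.30 = 44% | 20 points | 1.83 |
| 40% | 0.40 + 0.60 × 0.05 = 43% | 0.40 + 0.60 × 0.30 = 58% | 15 points | 1.35 |

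The analysis is mainly descriptive, so dilution is shown as differences and ratios rather than as power.

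**5. Timing.** If each dosing-day ECG fell at random within h hours, the chance that all three miss a window of w hours is (1 − w/h)³. For an assumed window of 2.5 hours (the infusion plus one hour):

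- h = 24: (1 − 2.5/24)³ = 72%
- h = 10: (1 − 2.5/10)³ = 42%

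For windows of 1 to 4 hours the range is 22% to 88%. If all three are taken before the infusion, all three miss.

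**6. Day lists.** Day 1 is in the calendar, Protocol 12.4 and SAP 7.3. It is absent from Protocol 1.11, Protocol 6.2 and SAP 2.6.

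**The case against.** The SAP already does much of this. SAP 7.3 shows the baseline percentage beside the study days, by arm. Table 11.1.1 reports, by dose, patients whose QTc rose more than 60 msec from baseline. SAP 7.1 includes QT-QTc among the parameters assessed for change in grade. Table 11.7.5 crosses baseline with worst later result and has a row and column for other abnormalities. Grade 3 or higher QT-QTc prolongation is a separate primary component. Under Protocol 11.2.5, ECG results that worsen and are judged clinically relevant are recorded as adverse events, which are tabulated by dose. Exclusion criterion 17 removes the most obvious confounders. On timing, ECGs are daily through Day 7, and Annex 7 reports that cardiac events in cancer patients did not correlate with any pharmacokinetic parameter explored.

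All of this stands as mitigation, but it leaves a gap. The baseline-referenced outputs concern QT, apart from the other-abnormality cells of Table 11.7.5. That table pools the cohorts, and a patient who stays in the other-abnormality category could have the same finding or a different one. Adverse event reporting catches only what the investigator considers relevant. Shells 11.7.2 to 11.7.4 are not in the available text, so a by-dose ECG table may exist there.

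Three stronger readings are tempting, and the documents do not support them:

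- **The endpoint mainly measures baseline prevalence.** No ECG rates are given, and step 3 goes either way.
- **The plan cannot separate drug effect from entry status.** The outputs above do so in part.
- **Chance imbalance at entry swamps the signal.** With b = 30%, the standard error of the difference in b between two arms is √(2 × 0.3 × 0.7/15) = 17 points, larger than a 10% rate of new findings. But the standard error of the difference in new findings at 10% is √(2 × 0.1 × 0.9/15) = 11 points, also larger than 10%. The comparison reflects 15 patients per arm and would count equally against the repaired endpoint.

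**Conclusion.** The point holds in limited form, as a cheap improvement. The ECG component does not distinguish new or worsened findings from those present at entry, and eligibility allows some. Entry prevalence can therefore inflate the percentages and narrow a dose contrast. The amount is unknown; under the assumed rates in step 4, a 25-point difference shrinks to 20 or 15 points. The SAP covers QT reasonably well. What is missing from the available text is a by-dose comparison of PR and other non-QT findings with each patient's own baseline.

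The timing gap is also real: the calendar permits every dosing-day ECG to precede the infusion. Whether an effect would be missed depends on whether ECG changes follow concentration, which the documents do not establish. The Day 1 mismatch is a plain inconsistency and mostly editorial, since the analysis list contains the endpoint list.

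**What to change.** 1. Add to the endpoint and to SAP 7.3 the number and percentage of patients with an ECG abnormality new or worse than the last pre-dose ECG, by dose arm and day, among patients with a baseline ECG. Define abnormality and worse, for example normal to abnormal, not clinically significant to significant, or a new type of finding. Present Table 11.7.5 by dose as well as pooled. This uses data already collected and costs SAP wording and programming.
2. Take the already scheduled Day 1 to 3 ECGs at one consistent time after the end of infusion and record that time, with the pre-dose ECG as baseline. This needs no additional ECGs. The cost is a fixed recording time on three days, and sites that now record before the infusion would no longer have that reading on Days 2 and 3. For ECGs already taken, report the clock time relative to the infusion where it was recorded.
3. Make the day list the same in Protocol 1.11, 6.2, 10 and 12.4 and in SAP 2.6 and 7.3, and state whether the Day 1 ECG is a baseline or an on-treatment reading. This is an editorial change.
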